10.1.9. Source documents

- Source documents provide evidence for the existence of the participant and substantiate the integrity of the data collected. Source documents are filed at the investigator's site.

- Data reported on the eCRF or entered in the eCRF that are transcribed from source documents must be consistent with the source documents or the discrepancies must be explained. The investigator may need to request previous medical records or transfer records, depending on the study. Also, current medical records must be available.
- Definition of what constitutes source data and its origin can be found in the source data acknowledgment.
- The investigator must maintain accurate documentation (source data) that supports the information entered in the eCRF.
- The sponsor or designee will perform monitoring to confirm that data entered into the eCRF by authorized site personnel are accurate, complete, and verifiable from source documents; that the safety and rights of participants are being protected; and that the study is being conducted in accordance with the currently approved protocol and any other study agreements, ICH GCP, and all applicable regulatory requirements.

10.1.10. Study and site start and closure

Start of study and first act of recruitment

The start of study and the first act of recruitment are defined as FSFV (first ICF signature date) at a country-level.

Study/Site Termination

GSK/ViiV Healthcare or designee reserves the right to close the study site or terminate the study at any time for any reason at the sole discretion of GSK/ViiV Healthcare. Study sites will be closed upon study completion. A study site is considered closed when all required documents and study supplies have been collected and a study-site closure visit has been performed.

The investigator may initiate study-site closure at any time, provided there is reasonable cause and sufficient notice is given in advance of the intended termination.

Reasons for the early closure of a study site by the sponsor or investigator may include but are not limited to:

For study termination:

- Discontinuation of further study intervention development

For site termination:

- Failure of the investigator to comply with the protocol, the requirements of the IRB/IEC or local health authorities, the sponsor's procedures, or GCP guidelines
- Inadequate or no recruitment (evaluated after a reasonable amount of time) of participants by the investigator
- Total number of participants included earlier than expected

If the study is prematurely terminated or temporarily suspended, the sponsor shall promptly inform the investigators, the IECs/IRBs, the regulatory authorities, and any contract research organization(s) used in the study of the reason for termination or temporary suspension, as specified by the applicable regulatory requirements. The investigator shall promptly inform the participant and should assure appropriate participant therapy and/or follow-up.

10.1.11. Publication policy

The results of this study may be published in peer reviewed scientific literature and/or presented at scientific meetings. The sponsor will comply with the requirements for publication of study results in accordance with standard editorial and ethical practice and as per the sponsor's internal policy. Authorship will be determined by mutual agreement and in line with ICMJE authorship requirements.

10.2. Appendix 2: Clinical laboratory tests

- The tests detailed in [Table 10](#) will be performed by the central laboratory.
- Local laboratory results are only required in the event that the central laboratory results are not available in time for either study intervention administration and/or response evaluation. If a local sample is required, it is important that the sample for central analysis is obtained at the same time. Additionally, if the local laboratory results are used to make either a study intervention decision or response evaluation, the results must be recorded in the eCRF.
- Protocol-specific requirements for inclusion or exclusion of participants are detailed in Section [5](#) of the protocol.
- Additional tests may be performed at any time during the study as determined necessary by the investigator or required by local regulations.
- Investigators must document their review of each laboratory safety report.

Table 10 Protocol-required safety laboratory tests

| Hematology | | | |
|---------------------------------------|------------|-----------------------------|---|
| Platelet count | | Automated WBC differential: | |
| RBC count | | Neutrophils | |
| WBC count (absolute) | | Lymphocytes | |
| Hemoglobin | | Monocytes | |
| Hematocrit | | Eosinophils | |
| MCV | | Basophils | |
| Clinical Chemistry^a | | | |
| BUN | Potassium | AST | Total and direct bilirubin |
| Creatinine | Chloride | ALT | Albumin |
| Glucose ^a | Cystatin C | Alkaline phosphatase | Creatine phosphokinase |
| Sodium | Lipase | Phosphate | eGFR ^b |
| Calcium | GGT | Protein | Lipid profile ^a (Total cholesterol, HDL, LDL, Triglycerides) |

| Routine Urinalysis | | | |
|--|--------------------------------|-----------|--------------|
| Specific Gravity | pH | Glucose | Protein |
| Blood | Ketones | Bilirubin | Urobilinogen |
| Nitrite | Leukocyte esterase by dipstick | | |
| Microscopic examination if blood or protein is abnormal | | | |
| Other Tests | | | |
| Plasma HIV-1 RNA | | | |
| CD4+ and CD8+ cell count | | | |
| Serology: HIV antibody, HbsAg, anti-HBc, anti-HBs and HBV DNA (by PCR) if indicated, and hepatitis C antibody, with reflex to HCV RNA (by PCR) if positive (Screening) ^d | | | |
| Syphilis RPR | | | |
| Urine drug screen (to include at a minimum amphetamines, barbiturates, cocaine, opiates, marijuana, heroin, cannabinoids and benzodiazepines, buprenorphine, fentanyl, methadone) | | | |
| Follicle stimulating hormone (FSH) and estradiol (only for instances when postmenopausal status is questionable) | | | |
| 
a) Glucose and lipid profile can be non-fasting except on Days 1, 8 and 25, as indicated in Section 1.3.
 
b) Glomerular filtration rate (eGFR) will be estimated by the central laboratory using the refitted, race-neutral Chronic Kidney Disease Epidemiology Collaboration (CKD-EPIcr_R) method [Delgado, 2022]. In addition, GFR will be estimated by the central laboratory using the refitted, race-neutral CKD-EPI-cystatin C [Delgado, 2022] at Day 1 and when indicated by renal toxicity criteria.
 
c) For fasting lipids assessments, an overnight fast is preferred; however, a minimum of a 6-hour fast is acceptable for participants with afternoon appointments.
 
d) HBV DNA will only be performed for participants with a positive anti-HBc and negative HbsAg and negative anti-HBs (past and/or current evidence).
 
e) Details of liver chemistry stopping criteria and required actions and follow-up assessments after liver stopping or monitoring event are given in Section 7.1.1 and Section 10.6. In addition, the laboratory may perform Hepatitis E IgM and Cytomegalovirus IGM if required in the event of a liver event. All events of ALT $\geq 3 \times$ upper limit of normal (ULN) and total bilirubin $\geq 2 \times$ ULN ($>35\%$ direct bilirubin) or ALT $\geq 3 \times$ ULN and INR > 1.5, if INR measured, which may indicate severe liver injury (possible Hy's law), must be reported to GSK/ViiV Healthcare in an expedited manner (excluding studies of hepatic impairment or cirrhosis).
 
f) Laboratory tests for eligibility may be performed by local laboratory in exceptional circumstances, however, central laboratory samples must also be collected at the screening visit. The results of each test used for eligibility must be entered in the eCRF.
 | | | |
| The addresses of the clinical laboratories in charge of human biological sample testing are provided in a separate document ('List of clinical laboratories used for human biological sample analysis') and stored in TMF at the time of the protocol finalization. | | | |

10.3. Appendix 3: AEs and SAEs: Definitions and procedures for recording, evaluating, follow-up, and reporting**10.3.1. Definition of AE**

| AE definition |
|---|
| 
• An AE is any untoward medical occurrence in a clinical study participant, temporally associated with the use of a study intervention, whether or not considered related to the study intervention. 
NOTE: An AE can therefore be any unfavorable and unintended sign (including an abnormal laboratory finding), symptom, or disease (new or exacerbated) temporally associated with the use of a study intervention.
 |

| Events Meeting the AE Definition |
|---|
| 
• Any abnormal laboratory test results (hematology, clinical chemistry, or urinalysis) or other safety assessments (e.g., ECG, radiological scans, vital signs measurements), including those that worsen from baseline, considered clinically significant in the medical and scientific judgment of the investigator (i.e., not related to progression of underlying disease).• Exacerbation of a chronic or intermittent pre-existing condition including either an increase in frequency and/or intensity of the condition.• New condition detected or diagnosed after study intervention administration even though it may have been present before the start of the study.• Signs, symptoms, or the clinical sequelae of a suspected intervention- intervention interaction.• Signs, symptoms, or the clinical sequelae of a suspected overdose of either study intervention or a concomitant medication. Overdose per se will not be reported as an AE/SAE unless it is an intentional overdose taken with possible suicidal/self-harming intent. Such overdoses should be reported regardless of sequelae.• Events that occur as a result of protocol-mandated procedures (i.e. invasive procedures, modification of participant's previous therapeutic regimen).• "Lack of efficacy" or "failure of expected pharmacological action" per se will not be reported as an AE or SAE. Such instances will be captured in the efficacy assessments. However, the signs, symptoms, and/or clinical sequelae resulting from lack of efficacy will be reported as AE or SAE if they fulfill the definition of an AE or SAE. |

Events NOT Meeting the AE Definition

Any clinically significant abnormal laboratory findings or other abnormal safety assessments that are associated with the underlying disease, unless judged by the investigator to be more severe than expected for the participant's condition.

The disease/disorder being studied or expected progression, signs, or symptoms of the disease/disorder being studied, unless more severe than expected for the participant's condition.

Medical or surgical procedure (e.g., endoscopy, appendectomy): the condition that leads to the procedure is the AE.

Situations in which an untoward medical occurrence did not occur (social and/or convenience admission to a hospital, admission for routine examination.).

Anticipated day-to-day fluctuations of pre-existing disease(s) or condition(s) present or detected at the start of the study that do not worsen. Pre-existing diseases will be recorded in the medical history section of the eCRF.

Hospitalization for elective treatment of a pre-existing condition (known or diagnosed before signing the informed consent) that did not worsen from baseline.

DRE typically associated with the disease under study. These events will be recorded in the participant's eCRF and will be monitored by the SRT on a routine basis.

However, if 1 or both of the following conditions apply, then the event should be reported promptly to GSK as an SAE (see Section [8.4.8](#)):

The event is, in the investigator's opinion, of greater intensity, frequency, or duration than expected for the individual participant, or

The investigator considers that there is a reasonable possibility that the event was related to the administration of the study intervention

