| | | | | | | | | | | | | | 55 years in first degree relatives only See Section 8.1.2 for more information |
| Prior ART check to ensure naïve status | X | | | | | | | | | | | | |
| CDC classification | X | X | | | | | | | | | | | See Section 8.2 for more information |
| HIV-associated conditions | X | X | X | X | X | X | X | X | X | X | X | | See Section 8.2 for more information |
| Plasma for HIV-1 genotype/phenotype ⁴ | | X | X | X | | X | | X | X | X | X | | See Section 8.8 for more information |
| HIV-1 RNA | X | X | X | X | | X | | X | X | X | X | X | See Section 8.2 for more information |
| Physical examination including height and weight ⁵ | X | X | | | | | | X | | | | X | See Section 8.3.1 for more information |
| Vital signs | X | X | X | X | | X | | X | X | X | X | X | See Section 8.3.2 for more information |
| C-SSRS Administration | X | | | | | | | X | | | | X | See Section 8.3.6 for more information |
| ECG: single reading | X | | | | | | | | | | | | See Section 8.3.3 for more information |

CONFIDENTIAL

212580

Protocol Amendment 1 Final

| Procedure ¹ | Screening ² (7-14 days before Day 1) | Study Intervention Period Days 1-7 | | | | | | Post-Study Intervention Follow-up Days 8-21 | | | Follow-up/ED ¹⁵ | Notes ED = early discontinuation/withdrawal | |
|---|--|------------------------------------|----------------|---|-----------------------|---|-----------------------|---|----------------|-----------------------|----------------------------|--|---|
| | | Day 1 | Day 2 | Days 3 and 4 1 clinic visit and 1 virtual ³ | | Days 5 and 6 1 clinic visit and 1 virtual ³ | | Day 7 | Day 8 | Day 14 (+/- 1 day) | Day 21 (+/- 1 day) | | |
| | | Clinic visit 1 | Clinic visit 2 | Clinic visit 3 | Virtual ¹⁴ | Clinic visit 4 | Virtual ¹⁴ | Clinic visit 5 | Clinic visit 6 | Clinic visit 7 | Clinic visit 8 | Clinic visit 9 | |
| ECG: single reading pre-dose ¹³ | | | X | X | | X | | X | X | | | X | See Section 8.3.3 for more information |
| ECG: triplicate reading pre-dose | | X | | | | | | | | | | | See Section 8.3.3 for more information |
| ECG: single reading post-dose at 5, 7, 8 and 9 h | | X | | | | | | X ⁶ | | | | | See Section 8.3.3 for more information |
| Confirmation of PONCBP (female participants) | X | | | | | | | | | | | | See Section 10.4.1.1 for more information |

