8.4.7. Disease-related events and/or disease-related outcomes not qualifying as AEs or SAEs

The DREs listed in the CDC Classification System for HIV-1 Infections (Section 10.9) are common in participants living with HIV-1 and can be serious/life threatening:

Because these events are typically associated with the disease under study, they will not be reported according to the standard process for reporting of SAEs even though the event may meet the definition of an SAE. These events will be recorded on the HIV-associated conditions eCRF page if they occur, according to the timeframe defined in the CRF completion guidelines. These DREs will be monitored by a SRT on a routine basis.

NOTE: However, if any of the following conditions applies, then the event must be recorded and reported as an AE/SAE (instead of a DRE):

The event is, in the investigator's opinion, of greater intensity, frequency, or duration than expected for the individual participant.

OR

The investigator considers that there is a reasonable possibility that the event was related to study intervention.

OR

Death occurring for any reason during a study, including death due to a disease-related event, will always be reported promptly.

OR

Lymphomas and invasive cervical carcinomas are excluded from this exemption; they must be reported as SAEs even if they are considered to be HIV-related.

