#### **6.1.2. Demographic and Baseline Characteristics**

The demographic characteristics including age, gender, ethnicity, race, height, weight and BMI at baseline will be summarized with descriptive statistics. In addition, the following age categories will be summarized: 18-64, 65-84 and  $\geq 85$  based on the Enrolled Analysis Set.

Demographic data will be listed.

Other baseline characteristics data such as medical history, CDC HIV-1 classification will be available at participant-level via RAPIDO DV. Participant-level HIV-1 associated conditions and pregnancy data will also be available via RAPIDO DV.

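### Protocol Sections 8.4.7 and 10.3.1 classify the same non-serious disease-related event differently, so the Day 8 SAE count can depend on which section a site follows

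*Protocol*

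**What the plan says.** Protocol Section 8.4.7 exempts the conditions in the CDC list (Section 10.9): "they will not be reported according to the standard process for reporting of SAEs even though the event may meet the definition". They go on a dedicated eCRF page instead. Four conditions end the exemption: the event is worse than expected for that participant, it may be related to study intervention, it is a death ("Death occurring for any reason during a study, including death due to a disease-related event, will always be reported promptly"), or it is one of two named cancers ("Lymphomas and invasive cervical carcinomas are excluded from this exemption; they must be reported as SAEs even if they are considered to be HIV-related"). If any condition applies, "then the event must be recorded and reported as an AE/SAE (instead of a DRE").

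Protocol Section 10.3.1 repeats the exemption in its list of events that are not AEs, and gives only the first two conditions: "However, if 1 or both of the following conditions apply, then the event should be reported promptly to GSK as an SAE". Section 10.3.2 then defines an SAE by a list of outcomes and situations.

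The secondary safety endpoint (Protocol Section 3.1; SAP Section 4.3.1) counts SAEs, deaths and AEs that lead to discontinuation, up to Day 8. AEs up to Day 25 are exploratory.

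In the Schedule of Activities, the row "HIV-associated conditions" is marked from Screening to Day 21 and is blank in the Day 25/ED column. On analysis, SAP Section 6.1.2 states: "Participant-level HIV-1 associated conditions and pregnancy data will also be available via RAPIDO DV".

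**The concern.** A reporting rule should send a given event to one place. Here a listed event that is worse than expected or possibly related, but meets no seriousness criterion, has two destinations. Section 8.4.7 makes it an AE, taking the slash in AE/SAE to be settled by the criteria in 10.3.2. Section 10.3.1 makes it an SAE outright.

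Sites can reasonably land on either text. Section 8.4 holds the body rule but sends readers to 10.3 for definitions, and the Schedule of Activities points AE and SAE review to 10.3.7, also in Appendix 3.

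What is at stake is a named secondary endpoint in cohorts of about six, where one participant is a visible share. An SAE also carries the 24-hour reporting duty of Section 8.4.1.

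**Working it through.** The plan states no figure on this point, so there is none to reproduce. The check sets the two rules side by side, then sizes one reclassified participant.

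**Step 1: the two rules, case by case**

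| CDC-listed event | Section 8.4.7 | Section 10.3.1 |
|---|---|---|
| No condition met | Exempt | Exempt |
| Worse than expected or possibly related; serious | SAE | SAE |
| Worse than expected or possibly related; not serious | AE | SAE |
| Lymphoma or invasive cervical carcinoma, as expected and unrelated | SAE | Not named |
| Death | Reported promptly | Not named |

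Section 8.4.7 has four triggers and 10.3.1 has two, both shared. The third row is a direct conflict. The last two are omissions.

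**Step 2: 10.3.1 against its neighbours**

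The same list in 10.3.1 says that manifestations of the disease under study are not AEs unless more severe than expected, which implies that the more severe ones are AEs. Section 10.3.7.2 says an event is serious when it meets at least one of the predefined SAE outcomes. Neither fits a rule that makes every such event an SAE.

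**Step 3: can the case occur?**

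Exclusion criterion 1 (Section 5.2) bars active Stage 3 disease but allows cutaneous Kaposi's sarcoma that needs no systemic therapy. Kaposi's sarcoma is on the list in Section 10.9. Worsening beyond expectation, without a seriousness criterion, falls in the third row.

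**Step 4: size**

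Inputs: 6 per active cohort (Protocol Section 4.1); active participants 3 × 6 in Part 1 plus 6 in Part 2 = 24 (SAP Section 1.2). Incidence is x/n, with exact (Clopper-Pearson) 95% intervals.

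- Cohort of 6: 0/6 = 0% (0 to 45.9); 1/6 = 16.7% (0.4 to 64.1).
- All active: 0/24 = 0% (0 to 14.2); 1/24 = 4.2% (0.1 to 21.1).

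The documents give no rate for such events. Assuming a probability p per participant through Day 8, the chance of at least one affected participant is 1 − (1 − p)^n:

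| Assumed p | n = 6 | n = 24 |
|---|---|---|
| 0.5% | 3% | 11% |
| 1% | 6% | 21% |
| 2% | 11% | 38% |
| 5% | 27% | 71% |

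**Step 5: the schedule row**

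The row has 11 of 12 visit columns marked; the unmarked one is Day 25/ED. The HIV-1 RNA row carries a mark in that column, so the blank is not a misaligned table. Section 7.1.4 requires withdrawal after any missed dose, so an ED visit can fall before Day 8, with no scheduled check for the exempt events.

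**The case against.** The strongest reply is that 10.3.2 and 10.3.7.2 already define seriousness, so a careful site would not call a non-serious event an SAE. SAP Section 4.3.1.2 also provides a listing of all AEs and one of the reasons for considering an event an SAE, so a misfiled event could be noticed. Eligibility (CD4 count of at least 200, no active Stage 3 disease apart from the Kaposi's exception) keeps such events rare, and safety is only described, not tested. All of this limits the effect. It does not remove the conflict: the instruction in 10.3.1 is explicit, and the SAE table counts what sites report.

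Three stronger readings are tempting, and the documents do not support them.

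- **That deaths or lymphomas escape reporting.** Death is an SAE criterion in 10.3.2 and a separate component of the endpoint. Section 8.4.7 is explicit on the two cancers, and the appendix's silence does not override it. Appendix 3 also gives invasive or malignant cancers as examples of events usually considered serious, and exclusion criterion 2 restricts ongoing malignancy at entry.
- **That the blank Day 25/ED cell drives the SAE endpoint.** The endpoint closes at Day 8, and the row is marked at every visit and virtual contact up to then. SAEs are collected to final follow-up whatever that row shows (Section 8.4.1). Even at an ED visit before Day 8, what may be missed is mainly the recording of exempt events.
- **That exempt events appear in no table.** The SAP says they are available in a viewer, but it leaves details of displays to the OPS, which is not among the documents.

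**Conclusion.** The conflict is real and the text is wrong as written. For a listed event that is worse than expected or possibly related but not serious, 8.4.7 gives an AE and 10.3.1 an SAE. The two missing triggers make 10.3.1 an incomplete copy of the body rule, but have little practical effect.

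The size is one participant at a time: 16.7 percentage points in a cohort of 6 and 4.2 in 24 active participants, provided that participant has no other SAE by Day 8. The chances in Step 4 rest on assumed rates and show a range only.

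The blank Day 25/ED cell is a separate, minor gap in recording disease-related events. It gives no ground for doubting the Day 8 SAE count of a participant who stays on schedule.

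**What to change.** Reconcile the two sections into one rule. In Section 10.3.1, repeat the four conditions of 8.4.7 or replace the list with a cross-reference to it. Replace the instruction to report such events as SAEs with one to report them as an AE or an SAE according to the seriousness criteria in 10.3.2.

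Separately, mark HIV-associated conditions at Day 25/ED in the Schedule of Activities, or state why the cell is blank.

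The reporting-rule change costs only wording in one appendix. The schedule change is one cell at a visit that already takes place. No extra SAP table row is asked for: counting exempt events that meet the SAE definition would need seriousness data, which the documents do not show the HIV-associated conditions page to collect.
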